Official Title of the study: Effect of Kefir on Appetite

NCT number: NCT03636217

Document Date: 21 October 2016 (The date on which the uploaded document was approved by a human subjects protection review board.)

1. Background

Obesity is one of the global public health problems in spite of all efforts of the scientific community and public health strategies. In the most recent World Health Organization data, 39% and 13% of adults aged 18 years and over were reported as overweight and obese respectively (W.H.O., 2016). Obesity has been also shown to be associated with a range of health-related problems, including hypertension, dyslipidaemia, type 2 diabetes, cardiovascular disease, and cancer (Guh, et al., 2009). Recently, low-glycaemic index (GI) diets have been recommended as an alternative dietary approach for managing obesity and its associated comorbidities, because they may be more effective than traditional energy-restricted low-fat diets at reducing body weight and controlling glucose and insulin metabolism (Juanola-Falgarona, et al., 2014). In addition to improved glycaemic control, increased satiety or decreased food intake have been shown after consuming low-GI diets in short-term studies (Lennerz, et al., 2013; Zafar, Kabir, & Ghazai, 2011). However, obesity has been linked to low levels of physical activity and Western-style diets, enriched in high-GI foods such as highly refined carbohydrates, sugary beverages, etc. (Varlamov, 2017). Thus, strict adherence to low-GI diets may be difficult for obese people who consumed the Western-style diets for a long time.

On the other hand, recent studies have suggested that gut microbiota may be a novel factor involved in body weight management, and play a role by the regulation of energy harvest, fat storage and appetite (Firouzi, 2018; Pimenta, et al., 2018). Therefore, the gut microbiota modulation using pre- or probiotics has led to much interest in its therapeutic potential. Dietary intervention studies have unveiled that probiotics may help to lose weight by providing appetite control (Belguesmia, et al., 2016), and reducing food intake (Zoumpopoulou, Pot, Tsakalidou, & Papadimitriou, 2017). However, it has been yet unknown the potential effects of probiotics combined with low- or high-GI meals/diets on satiety or voluntary food intake.

2. Objective

The aim of this study was to determine whether kefir, a natural probiotic, would have provided any beneficial effect on appetite sensations and subsequent food intake, when consumed with low- or high-GI meals.

3. Materials and methods

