3.3. Study design

This was a randomized, single-blind, 3-intervention crossover trial conducted on 3 separate days, with a 1-week washout period between each study day. All participants were randomly submitted to three different test meals with the following different GI amounts and milk or kefir: a low-GI and milk content (LGI-Milk), a low-GI and kefir content (LGI-Kefir), and a high-GI and kefir content (HGI-Kefir). The order of the test meals was determined by using a computer-generated randomization sequence before recruitment. The primary outcomes were appetite sensations and subsequent food intake. Desire for specific food types and palatability of test meals were the secondary outcomes.

Participants received each test meal in a randomly assigned order on three different mornings separated by a washout period of 1-week when they were asked to maintain their usual diet and physical activity. On the day before each test meal, participants were instructed to eat a standard evening meal at 21:00 h and to refrain from eating and/or drinking (except for water) and/or doing any physical activity beyond that of their typical daily activities. Moreover, participants were tested within the follicular phase of their menstrual cycle (3–10 d after onset of menses) to avoid possible influences of menstrual cycle phase on hormonal changes and appetite (Chowdhury, Richardson, Tsintzas, Thompson, & Betts, 2015).

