3.4. Test meals composition

All test meals were matched for energy, LGI-Milk and LGI-Kefir meals also for macronutrients and GI, but HGI-Kefir meal had a nearly 2-fold difference in GI (Table 1). Furthermore, both milk and kefir drinks contained 120mg/100ml calcium, and kefir drink also had 107 CFU/g

probiotic bacteria (*Lactobacillus* spp. and *Streptococcus* spp.). The energy content of test meals (~445 kcal) were estimated as corresponding to about 25% daily energy needs of a sedentary female (Chowdhury, et al., 2015), and the daily energy needs were also calculated by the Schofield equation, taking into account: gender, age, weight and a physical activity level of 1.3.

Table 1. Nutritional composition and glycaemic index of the component foods in test meals

	Portion size (g/ml)	Energy (kJ[kcal])	AvCHO* (g)	Protein (g)	Fat (g)	GI (%)
LGI-Milk						
Milk (full-fat)	200	524(125)	9.9	5.8	6.8	31
Cheddar cheese	25	424(101)	0.0	6.4	8.5	0
Apple	200	469(112)	24.9	0.9	0.9	36
Grain bread	50	435(105)	19.1	4.8	0.9	50
Toplam		1852(443)	53.9	17.9	17.1	40
LGI- Kefir						
Kefir (full-fat, plain)	200	526(126)	10.0	5.8	6.3	36
Cheddar cheese	25	424(101)	0.0	6.4	8.5	0
Apple	200	469(112)	24.9	0.9	0.9	36
Grain bread	50	435(105)	19.1	4.8	0.9	50
Toplam		1854(444)	54.0	17.9	16.6	41
HGI- Kefir						
Kefir (full-fat, plain)	200	526(126)	10.0	5.8	6.3	36
Raspberry jam	50	568(136)	31.8	1.7	0.0	78
White bread	75	773(185)	34.0	7.0	1.5	70
Toplam		1868(447)	75.8	14.5	7.9	70

*AvCHO, available carbohydrate including sugars and starch, excluding fiber.

GI of foods in test meals was estimated by using the GI tables, with glucose as the reference food (Bao, Atkinson, Petocz, Willett, & Brand-Miller, 2011). The average meal GI was calculated as follows:

$$\text{Meal GI} = \frac{\sum_{a=1}^N (\text{GI}_a \times \text{AvCHO}_a \times \text{Frequency}_a)}{\sum_{a=1}^N (\text{AvCHO}_a \times \text{Frequency}_a)}$$

where n is the number of foods consumed, GI_a is the GI for food a, AvCHO_a is the available carbohydrate content per serving of food a, and Frequency_a is the consumption frequency of one serving of food a during the meal.

3.5. *At libitum lunch*

At 180 min after the test breakfast, participants were presented with the ad libitum lunch following appetite measurements. Frequently consumed foods were used to prepare the lunch consisting of pasta with tomato sauce, yogurt drink and mandarin. Participants were asked to

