4.1. Sample size

A power-based sample size calculation based on previous research from Stevenson et al. (Stevenson, Astbury, Simpson, Taylor, & Macdonald, 2009) revealed that 21 participants were needed to provide 80% power to detect 5% difference between groups in primary outcomes. To allow discontinuation during the study, 24 participants (considering 15% losses) were recruited, and the study was concluded with 22 participants.

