4.2. Data analysis

Statistical analysis was performed using the Statistical Package for the Social Sciences (version 22.0; IBM SPSS Statistics) software. Data were expressed as the mean \pm SD unless otherwise indicated. Normality was assessed using the histogram and normal Q-Q plots, and also Shapiro-Wilk test. Furthermore, continuous variables were examined for skewness and kurtosis, and log-transformed before analysis and reported back-transformed geometric means (G) \pm standard error (S.E) when required (Akin, et al., 2015). Postprandial appetite sensations were quantified as area under the curve (AUC) calculated according to the trapezoidal rule. One-way (1-factor) analysis of variance (ANOVA) for repeated measures was applied to determine statistical differences between groups. In addition, the data were analysed by using 2-factor (time x meal) repeated-measures ANOVA, and Bonferroni post hoc tests were applied to significant time x

meal interactions. For all statistical analyses, p values less than 0.05 were considered to have statistical significance.

REFERENCES

Chang, K. T., Lampe, J. W., Schwarz, Y., Breymeyer, K. L., Noar, K. A., Song, X., & Neuhouser, M. L. (2012). Low glycemic load experimental diet more satiating than high glycemic load diet. *Nutr Cancer*, 64, 666-673.

Chowdhury, E. A., Richardson, J. D., Tsintzas, K., Thompson, D., & Betts, J. A. (2015). Carbohydrate-rich breakfast attenuates glycaemic, insulinaemic and ghrelin response to ad libitum lunch relative to morning fasting in lean adults. *Br J Nutr*, 114, 98-107.

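### The objective asks about kefir with low- or high-GI meals, but there is no high-GI milk meal, and the one contrast that isolates kefir is not specified for AUC or lunch intake

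*Combined protocol and SAP*

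**What the plan says.** - **Objective (section 2).** The study is to determine whether kefir "would have provided any beneficial effect on appetite sensations and subsequent food intake, when consumed with low- or high-GI meals".
- **Design (section 3.3).** "This was a randomized, single-blind, 3-intervention crossover trial conducted on 3 separate days". The meals are LGI-Milk, LGI-Kefir and HGI-Kefir. There is no HGI-Milk meal. "The primary outcomes were appetite sensations and subsequent food intake".
- **Meals (section 3.4).** "All test meals were matched for energy, LGI-Milk and LGI-Kefir meals also for macronutrients and GI". HGI-Kefir is matched on energy only, and Table 1 prints its composition.
- **Analysis (section 4.2).** Postprandial appetite is summarised as a trapezoidal AUC. "One-way (1-factor) analysis of variance (ANOVA) for repeated measures was applied to determine statistical differences between groups". A time-by-meal repeated-measures ANOVA is added, and "Bonferroni post hoc tests were applied to significant time x" meal interactions. No other follow-up test, reference meal or primary contrast is named.
- **Sample size (section 4.1).** The target difference is described only as being between groups, with no pair of meals named, and "the study was concluded with 22 participants".

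**The concern.** There are two linked gaps.

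First, a kefir effect needs a comparator without kefir at each GI level that the objective mentions, and the design supplies one only at low GI. HGI-Kefir minus LGI-Kefir holds the drink constant, so it carries no information on kefir. HGI-Kefir minus LGI-Milk changes the drink and the rest of the meal together.

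Second, the analysis treats meal as one three-level factor. The only pairwise rule depends on a time-by-meal interaction. AUC and lunch intake have one value per visit and no time term, so the rule does not reach them. What remains for these outcomes is a test of whether any meal differs from any other.

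At stake is the conclusion named in the study's title. A significant three-meal result for AUC or lunch intake could be reported as an effect of kefir when kefir has none, and a statement about kefir with high-GI meals would rest on no comparison at all.

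**Working it through.** **1. Which effects the three meals can estimate.** Write each meal mean in terms of m (milk at low GI), k (kefir), g (the high-GI meal) and kg (kefir-by-GI interaction):

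- LGI-Milk = m
- LGI-Kefir = m + k
- HGI-Kefir = m + k + g + kg

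Three means for four parameters: the design matrix has rank 3.

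| Effect | Expression | Estimable? |
|---|---|---|
| Kefir at low GI | k = LGI-Kefir − LGI-Milk | yes |
| High-GI vs low-GI meal, both with kefir | g + kg = HGI-Kefir − LGI-Kefir | yes |
| Kefir at high GI | k + kg | no |
| Interaction | kg | no |
| Kefir averaged over GI | k + kg/2 | no |

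More participants or another model cannot change the last three rows. Only setting kg = 0 by assumption would.

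**2. What HGI-Kefir minus LGI-Kefir compares (Table 1).** The plan's meal-GI formula returns its low-GI totals: LGI-Milk (31×9.9 + 36×24.9 + 50×19.1)/53.9 = 40.0 (stated 40), and LGI-Kefir (36×10.0 + 36×24.9 + 50×19.1)/54.0 = 41.0 (stated 41). For HGI-Kefir, (36×10.0 + 78×31.8 + 70×34.0)/75.8 = 68.9 (stated 70), a small gap that does not affect this point.

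| | HGI-Kefir | LGI-Kefir | Change |
|---|---|---|---|
| Fat, g | 7.9 | 16.6 | 7.9/16.6 − 1 = −52% |
| Protein, g | 14.5 | 17.9 | 14.5/17.9 − 1 = −19% |
| Available carbohydrate, g | 75.8 | 54.0 | 75.8/54.0 − 1 = +40% |
| Listed portions, g/ml | 200+50+75 = 325 | 200+25+200+50 = 475 | 325/475 − 1 = −32% |

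By contrast, LGI-Kefir minus LGI-Milk differs by 16.6 − 17.1 = −0.5 g fat, 54.0 − 53.9 = 0.1 g available carbohydrate, 0 g protein and 444 − 443 = 1 kcal.

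**3. How often the three-meal test is significant when kefir does nothing.** Inputs: n = 22 analysed (section 4.1), k = 3 meals (section 3.3), alpha 0.05 (section 4.2). The plan gives no SD, so the shift d of the HGI meal, in within-subject residual SDs, is assumed. Normal errors and sphericity are also assumed.

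Degrees of freedom are k − 1 = 2 and (n − 1)(k − 1) = 42; the critical F is 3.22. With true effects 0, 0 and d, the squared deviations from their mean d/3 sum to 2(d/3)² + (2d/3)² = (2/3)d², so the noncentrality is 22 × (2/3) × d².

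| d | Noncentrality | P(p < 0.05), noncentral F | Simulation, 40,000 trials |
|---|---|---|---|
| 0.25 | 0.92 | 12% | not run |
| 0.5 | 3.67 | 36.1% | 36.1% |
| 0.75 | 8.25 | 69.9% | 70.4% |
| 1.0 | 14.67 | 92.1% | 92.2% |

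In the simulations, the paired LGI-Kefir versus LGI-Milk test rejected in 4.9% to 5.0% of trials, as it should.

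**4. What the kefir contrast can deliver.** The stated 21 participants (80% power, 5% difference) cannot be reproduced, because no SD, test or pair of meals is given. If 21 was meant for one two-sided paired t test, the implied standardised difference is 0.643, so the SD of the within-person difference is 5%/0.643 = 7.8% of the mean. On that assumption, 22 participants give 82% power for one contrast at 0.05, and 66% if three pairwise contrasts each use 0.05/3 = 0.0167. If that SD is instead 5, 7.5, 10 or 15% of the mean, power for one contrast is 99%, 85%, 61% or 32%.

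**The case against.** **The objective can be read as a question about combinations.** Section 1 speaks of probiotics combined with low- or high-GI meals, and three whole meals can answer a whole-meal question. This softens the point but does not remove it, because section 2 asks whether kefir is beneficial and that needs a comparator without kefir.

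**The percentages are power, not an error rate.** With the HGI meal truly shifted, the three-meal null is false and rejecting it is correct. Harm comes only if the result is read as a kefir effect, and the plan nowhere says it will be. The range is also assumed: at 0.25 SD the figure is 12% and at 0.1 SD it is 6%. All of this stands. The figures show only that a significant three-meal test says little about kefir.

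**The SAP is silent rather than exclusionary.** Pairwise tests after the one-way ANOVA are not ruled out, and the Bonferroni tests can separate the two low-GI meals on appetite scores over time. That is true for the time-point scores. For AUC and lunch intake, silence leaves both the comparison and its multiplicity rule open to choice after the data are seen.

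**The macronutrient differences are disclosed.** They are, in section 3.4 and Table 1, and no passage claims a pure GI effect. But no limit on interpretation is drawn from them. The portion total also adds grams to millilitres, so it is only a rough guide.

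**Even the valid contrast needs a qualifier.** It compares kefir as a drink with milk as a drink: Table 1 lists drink GI as 36 against 31 and fat as 6.3 against 6.8 g. It does not isolate the bacteria.

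**Conclusion.** The concern holds, with high confidence, and needs correcting before conclusions are drawn. The high-GI half of the kefir objective has no estimator without a no-interaction assumption that the plan does not state. The low-GI half is validly designed, but its contrast is not specified for AUC or lunch intake. Both findings rest on the design and the text, not on any assumed number.

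The size of the possible misreading does depend on an assumption: 36% to 92% for HGI shifts of 0.5 to 1.0 residual SD, and less for smaller shifts. HGI-Kefir minus LGI-Kefir remains a legitimate comparison of two meals, but not of GI alone.

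**What to change.** 1. **Objective and conclusions.** Limit the kefir question to: *whether kefir, compared with milk, affects appetite and subsequent intake when consumed with a low-GI meal*. Because the document describes a concluded study, show this as a later narrowing of the aim and say that the high-GI part was not answered.
2. **Section 4.2.** Add: *For appetite AUC and lunch intake, the kefir effect is LGI-Kefir minus LGI-Milk, reported as a within-participant mean difference with 95% CI whatever the three-meal test shows.* Label it as specified after data collection if that is so. It would also help to state how multiplicity is handled across the appetite AUCs and lunch intake.
3. **High-GI meal.** Report HGI-Kefir minus LGI-Kefir as a whole-meal comparison with kefir held constant, not as a GI effect. Make no kefir claim at high GI or from HGI-Kefir versus LGI-Milk.

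The cost is wording plus one contrast from data already collected, with no extra meal or visit. The downside is a narrower claim, and a contrast that may have to be reported as not prespecified.

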3.1. Participants

Twenty four healthy, normal-weight (BMI 18.5–25 kg/m²) females, aged 21–24 years, were recruited from Erciyes University and the surrounding community. Exclusion criteria were following an energy-restricted diet during the last three months, change in body weight >5 kg during the last three months, lack of appetite, physician-diagnosed conditions or medications that influence metabolism, having any chronic diseases such as diabetes, hypertension etc., smoking, practicing endurance sports, having difficulties with swallowing/eating, hypersensitivity for the food products under study, being a vegan, and pregnant or lactating. Furthermore, one enrolled participant withdrew from the trial and the other one was not

included to the analysis of data because of influenza. Finally, leaving a total of 22 participants were assessed for the main outcomes (Fig. 1).

[figure not shown]

Figure 1. Participant recruitment flow diagram

3.2. Nutritional evaluation

Body weight and height of participants were obtained, and BMI was calculated. Waist and hip circumference were measured using a non-elastic tape with the participants standing, with the face directed towards, shoulders relaxed, and the tape was positioned at a level parallel to the floor.

Participants' dietary intakes were assessed by the a-24-hour dietary recall using a photographic atlas of food portion sizes to quantify the data in the beginning of study and on the day of each test meal. Diet composition was analysed by the BeBiS Nutrition Information System software version 7.2.

Physical activity level was evaluated simultaneously with dietary assessment by the International Physical Activity Questionnaire (IPAQ) short form, a validated survey instrument (Saglam, et al., 2010). The 7-item IPAQ records self-reported physical activity in the last seven

days. Responses were converted to Metabolic Equivalent Task (MET) minutes per week according to the IPAQ scoring protocol.

3.3. Study design

This was a randomized, single-blind, 3-intervention crossover trial conducted on 3 separate days, with a 1-week washout period between each study day. All participants were randomly submitted to three different test meals with the following different GI amounts and milk or kefir: a low-GI and milk content (LGI-Milk), a low-GI and kefir content (LGI-Kefir), and a high-GI and kefir content (HGI-Kefir). The order of the test meals was determined by using a computer-generated randomization sequence before recruitment. The primary outcomes were appetite sensations and subsequent food intake. Desire for specific food types and palatability of test meals were the secondary outcomes.

Participants received each test meal in a randomly assigned order on three different mornings separated by a washout period of 1-week when they were asked to maintain their usual diet and physical activity. On the day before each test meal, participants were instructed to eat a standard evening meal at 21:00 h and to refrain from eating and/or drinking (except for water) and/or doing any physical activity beyond that of their typical daily activities. Moreover, participants were tested within the follicular phase of their menstrual cycle (3–10 d after onset of menses) to avoid possible influences of menstrual cycle phase on hormonal changes and appetite (Chowdhury, Richardson, Tsintzas, Thompson, & Betts, 2015).

On the each testing day, participants arrived in the testing room at 08.30 h following a 12-h fast and anthropometric measurements were completed before eating the test meal. Also, first appetite scores were measured for baseline measurements (time zero). At 09:00 h participants received the test meal blinded to its nutritional characteristics and were asked to consume within 15 min. During the postprandial period, participants remained at rest in the testing room and appetite scale was applied at 15, 30, 60, 90, 120, 150 and 180 min. Moreover, participants were asked to assess the palatability of test meal at 15 min (immediately after consuming test meal). No food or drink other than water was allowed following consumption of the test meal until an ad libitum lunch. Water was available ad libitum throughout the first trial; however, the volume consumed was measured and the participants drank the same volume during the second and third trial. Participants were permitted to watch movies, read, or play with electronic devices (laptop computer, mobile phone etc.) or undertake other similar sedentary activities throughout each test day but were not allowed to sleep.

This study was conducted according to the guidelines laid down in the Declaration of Helsinki. All procedures were approved by the Clinical Research Ethics Committee of the Erciyes University (2016/547) on 21 October 2016, and all participants gave written informed consent. In addition, it was registered at ClinicalTrials.gov as NCT03636217.

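### The plan states no balance over the six meal orders and fits no visit term, so any visit effect stays as error in the LGI-Kefir minus LGI-Milk comparison

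*Combined protocol and SAP*

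**What the plan says.** Section 3.3 describes the design: "This was a randomized, single-blind, 3-intervention crossover trial conducted on 3 separate days, with a 1-week washout period between each study day". On allocation it says "The order of the test meals was determined by using a computer-generated randomization sequence before recruitment", and later "Participants received each test meal in a randomly assigned order on three different mornings separated by a washout period of 1-week". It mentions no blocking, Latin square or other restriction, and gives no number of women per order. Figure 1, the flow diagram, could not be read for this review and might hold those counts.

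Section 3.3 also makes visit 1 different from the others. "Water was available ad libitum throughout the first trial", and at visits 2 and 3 each woman had to drink the volume she had taken at visit 1.

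Section 4.1 states that "21 participants were needed to provide 80% power to detect 5% difference between groups in primary outcomes" and that "24 participants (considering 15% losses) were recruited, and the study was concluded with 22 participants".

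Section 4.2 plans a one-factor repeated-measures ANOVA and a time x meal repeated-measures ANOVA. Time there means minutes after the test meal, not visit. No visit (period) or sequence term is named.

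**The concern.** In a three-period crossover, a difference between visits is separated from the meal comparison in two ways: by the allocation (each meal equally often at each visit) and by the model (a visit term). The plan states neither. A visit effect is possible here because free choice of water became an imposed volume, and because the same lunch menu was met for the first, second and third time.

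Without a visit term, such an effect inflates the residual against which LGI-Kefir minus LGI-Milk is judged. If the orders were also unequal, it shifts the estimate by chance. There is little slack to absorb this: 21 women were needed and 22 were analysed.

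**Working it through.** **Inputs from the documents.** Three meals and three visits; 24 recruited, 22 analysed; 21 needed for 80% power to detect a 5% difference (section 4.1); "p values less than 0.05 were considered to have statistical significance" (section 4.2), taken here as two-sided.

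**The plan's own figure.** Allowing for 15% losses, 21/0.85 = 24.7 and 21 x 1.15 = 24.15. Both round up to 25, so the stated 24 is within one woman. The 21 cannot be reproduced, because no SD or within-woman correlation is given. Back-solving for n = 21 with a paired t test gives an SD of the paired difference of about 7.8% of the mean. The normal approximation gives 5 x sqrt(21)/(1.960 + 0.842) = 8.2%. I use 7.8%.

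**Orders.** 3! = 6 and 24/6 = 4, so exact balance was available. Under simple randomisation, the probability of exactly four per order is 24!/((4!)^6 x 6^24) = 0.07%.

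**Chance imbalance in visit.** Under simple randomisation, a woman's kefir visit number minus her milk visit number is -2, -1, 1 or 2 with probabilities 1/6, 1/3, 1/3 and 1/6.
- The variance is 4/6 + 1/3 + 1/3 + 4/6 = 2, so the mean over 22 women has SD sqrt(2/22) = 0.30 visits. By simulation it exceeds 0.3 in absolute value in 33% of draws and reaches 0.5 in 11%.
- With four women per order and two random losses, the SD is 0.09 and the maximum is 4/22 = 0.18. With all 24 it is exactly 0.

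**Effect of a linear drift b per visit, with no visit term.** The variance of the paired difference becomes 7.78^2 + 2b^2.
- b = 0: 60.5, SE = 7.78/sqrt(22) = 1.66.
- b = 2.5%: 60.5 + 12.5 = 73.0, SE = sqrt(73.0/22) = 1.82.
- b = 5%: 60.5 + 50 = 110.5, SE = sqrt(110.5/22) = 2.24.

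The variance ratios are 73.0/60.5 = 1.21 and 110.5/60.5 = 1.83.

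**Power for a 5% difference, 22 women.** The test uses the ANOVA residual (2 x 21 = 42 degrees of freedom; 40 with a visit term). The values are simulated and approximate.

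| Drift per visit (assumed) | No visit term, simple | No visit term, balanced | Visit term, either allocation |
|---|---|---|---|
| 0 | 83-84% | 83-84% | 81-84% |
| 2.5% | 77% | 78% | 81-84% |
| 5% | 59% | 60% | 81-84% |

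A paired t test on 21 degrees of freedom gives the same pattern: 82.0% without drift; 74.7% (simple) against 75.7% (balanced) at 2.5%; 56.4% against 57.0% at 5%.

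**Price of the visit term.** Relative to full balance, the variance of the adjusted contrast is multiplied by 1.05 on average under simple randomisation (about 1.12 at the 90th percentile) and by 1.004 with four per order and two losses. The 5% average is worth about one woman.

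**The case against.** The case against is substantial, and most of it limits the point rather than removing it.

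- A reader might infer that the orders were unconstrained, each woman's being drawn independently. The text does not say so. A list generated by computer in advance may equally have been blocked. Only the silence is established.
- A reader might infer bias. Under simple randomisation the visit shift is itself random and its variance is already in the reported SE; simulated type I error is 4.9-5.0%. What is lost is precision.
- A reader might infer that balancing the orders would cure the problem at no cost. Under the ANOVA as written it would not. Visit variation stays in the residual, power barely moves (77% to 78%, 59% to 60%), and the test becomes conservative, with type I error of about 3% at 2.5% drift and 1% at 5%. The visit term does the work.
- The drift is assumed. The documents give no estimate and it may be zero. At 5% per visit, visits 1 and 3 differ by 10%, twice the target difference, so that case is severe.
- The water rule equalises volume within each woman, and section 3.5 says the lunch was made of commonly eaten foods. Both make a large visit effect less likely. Neither excludes one, since choosing water freely and having it imposed remain different procedures. Section 3.3 also asks for weekly visits, which span 14 days, all within cycle days 3-10. Those statements need reconciling, and until they are, cycle day may differ by visit too.
- The text is in the past tense and the allocation can no longer be changed. That is correct, and it moves the remedy to the analysis and the reporting.

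**Conclusion.** The point holds as a reporting gap joined to an omitted model term. The documents do not state the type of randomisation, any restriction or the counts per order, and the analysis has no visit term although visit 1 was run differently. The consequence is extra random error in LGI-Kefir minus LGI-Milk, ranging from nothing (no visit effect) to a fall in power from about 83-84% to about 77% at 2.5% drift per visit and 59% at 5%. A visit term keeps power at about 81-84% throughout, whichever way orders were allocated.

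These figures assume a paired SD of 7.8% back-solved from n = 21, a single two-sided comparison at 0.05, linear drift, equal error variances and no carry-over. Severity is minor to moderate; the change is a cheap improvement and does not correct an invalid test.

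**What to change.** - **Section 4.2:** add visit (1, 2, 3) as a fixed effect, alongside woman and meal, to the model for each primary outcome, and base the LGI-Kefir minus LGI-Milk estimate and its interval on that model.
- **Section 3.3:** state the type of randomisation and any restriction, and report the number of women allocated to and analysed in each of the six orders.
- **Where a sequence is still to be drawn:** use permuted blocks of six over the six orders (four women per order with 24), together with the visit term and not instead of it.

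Cost: the visit of each meal is fixed by the woman's order, so no new data, women or visits are needed. The term uses two degrees of freedom. If orders prove unbalanced and there is no visit effect, it adds about 5% to the variance on average. With blocks, the last order in a block can be predicted by someone who knows the earlier ones, which matters little when every woman receives all three meals.

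### Three visits one week apart cannot all fall 3–10 days after onset of menses, so either the stated interval or the stated cycle-phase control needs correcting from the visit dates

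*Combined protocol and SAP*

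**What the plan says.** Section 3.3 describes a three-meal crossover "conducted on 3 separate days, with a 1-week washout period between each study day" and repeats that meals were given "on three different mornings separated by a washout period of 1-week". Neither sentence contains *at least* or a range.

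The same section states, without exception, that "participants were tested within the follicular phase of their menstrual cycle (3–10 d after onset of menses"), and gives the reason: "to avoid possible influences of menstrual cycle phase on hormonal changes and appetite". Appetite matters here because "The primary outcomes were appetite sensations and subsequent food intake".

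All participants were women, and section 3.1 reports two losses, "leaving a total of 22 participants were assessed for the main outcomes". It lists no criterion on cycle length or regularity.

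In section 4.2, "One-way (1-factor) analysis of variance (ANOVA) for repeated measures was applied to determine statistical differences between groups", and in addition "the data were analysed by using 2-factor (time x meal) repeated-measures ANOVA". The time factor there is time within a test session. Neither model contains visit order, cycle day or in-window status.

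**The concern.** The spacing rule and the cycle rule apply to the same three visits of the same women, and they do not fit together as written. The window is the only safeguard against cycle effects on appetite that the documents describe, and the analysis adjusts for nothing that could take its place.

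Two things are at stake. If visits were weekly, the protection was absent at some visits for every woman who completed the trial, and any cycle effect on appetite enters the error term of the primary analyses. If visits were spread over successive cycles, the washout was much longer than reported for at least one gap per woman. A reader or replicator cannot tell which trial was run.

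**Working it through.** **Inputs.** From section 3.3: 3 visits, a 7-day interval, and a window of days 3 to 10, which is 7 days from first to last. From section 3.1: 22 women analysed, so 22 × 3 = 66 visits. Cycle length L is not given; 21 to 35 days is assumed. The plan's implied figure is 3 of 3 visits inside the window.

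**1. Can all three visits fit?** Let the first visit be on day a, with 3 ≤ a ≤ 10.
- The second visit (a + 7) is in the same window only if a = 3, which gives day 10. The third is then day 17, which is in the next window only if 17 − L ≥ 3, so L ≤ 14.
- Otherwise the second visit must fall in the next window: a + 7 − L ≥ 3, so L ≤ a + 4 ≤ 14.

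So 3 of 3 is impossible for every L ≥ 15. Enumeration of all start days for L up to 60 gives the same answer. Counting the window as days 4 to 11 changes nothing, because the width is the same. Somewhat shorter gaps do not help within a cycle: even 4-day gaps span 8 days, more than 7.

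**2. If weekly spacing was kept.**
- Floor: one visit per woman outside, 22 of 66 (33%). At L = 28 this needs every woman to start on day 3 (days 3, 10, 17) or day 24 (days 24, 3, 10).
- Starts spread evenly over days 3–10, L = 28: in-window visits are 2, 1, 1, 1, 1, 1, 1, 1, mean 9/8 = 1.125. Inside: 22 × 1.125 = 24.75. Outside: 41.25 of 66 (62.5%).
- Start unrelated to the cycle, L = 28: of 28 start days, 6 give no in-window visit, 20 give one and 2 give two, mean 24/28 = 0.857. Inside: 18.9. Outside: 47.1 of 66 (71%).
- As above, but only women with at least one in-window visit: mean 24/22 = 1.091. Inside: 24. Outside: 42 of 66.

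**3. If the window was kept, with gaps of at least 7 days.** At most two visits fit in one cycle (days 3 and 10), so one gap must cross into the next cycle. The shortest such gap is (L + 3) − 10 = L − 7: 14, 21 or 28 days for L = 21, 28 or 35.

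**4. Size of the noise (illustration only).** The documents give no cycle effect and no SD. Assume a step shift of s within-woman SDs at every out-of-window visit. A woman with one or two of her three visits inside the window adds a sum of squares of (2/3)s² on 2 df, which is s²/3. A woman with none inside adds nothing, because all her visits shift together. With a fraction m of women mixed in this way, and meal order random:

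error variance ratio = 1 + m·s²/3

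| Case, L = 28 | Outside | s = 0.25 | s = 0.5 | s = 1.0 |
|---|---|---|---|---|
| Every woman has one or two in-window visits (m = 1) | about 41–42 of 66 | 1.02 | 1.08 | 1.33 |
| Start unrelated to cycle (m = 22/28) | 47 of 66 | 1.02 | 1.07 | 1.26 |

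More visits outside does not mean more noise: the second row has the higher count and the lower variance. At L = 35, m = 22/35 and the s = 1.0 figure is 1.21.

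In terms of power, take the 80% in section 4.1 as the no-shift value and use Φ(2.802/√r − 1.960), where r is the variance ratio. This gives about 79% at r = 1.02, 77% at 1.08, 70% at 1.26 and 68% at 1.33.

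**The case against.** The strongest reply is that a washout is often understood as a minimum. If visits were at least a week apart and booked in successive cycles, the window was respected, the washout was adequate, and only the interval is loosely described. This stands as a possibility. It is not the plainest reading, since the interval is given twice as one week and nothing mentions visits over several cycles, but the documents do not rule it out.

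The second reply is that randomized meal order protects the comparison. That also stands. Cycle phase would be linked to visit order, not to the meal, so no systematic advantage to any meal is expected. The variance figures rest on assumed shifts and a step-shaped effect, and none of them can be preferred from the documents. At the smaller shifts the loss of power is slight.

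A reader might go further and infer that the cycle control failed, that the meal comparisons are biased, or that the cycle statement should be withdrawn. The documents support none of these. They show that the two statements conflict, not which one is wrong. Practice may also have varied between women: if k of the 22 kept weekly spacing, at least k of 66 visits were outside the window.

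**Conclusion.** The point holds as an inconsistency in a stated design property and should be fixed. For exact 7-day spacing, the arithmetic needs no assumption beyond a cycle of 15 days or longer. The consequence depends on facts not in the documents. With weekly spacing, at least 22 of 66 visits were outside the window and phase control cannot be claimed for them. With the window kept, there is no validity problem from cycle phase and only the interval needs correcting. Where visits were outside, the expected effect is mainly added within-woman noise of unknown size; the ratios of 1.02 to 1.33 are conditional on assumed shifts and are not estimates.

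**What to change.** 1. From the visit dates and any recorded onset-of-menses dates, correct whichever statement is inaccurate. If true, a suitable wording is: *Visits were at least 1 week apart (median and range in days); x of 66 visits took place 3–10 d after onset of menses.*
2. Claim cycle-phase control only for visits where the dates show it. If onset dates were not recorded, say that compliance with the window cannot be documented.
3. Only if some visits were outside the window, add cycle day or in-window status to a within-participant mixed model for the primary outcomes, as a sensitivity analysis. Do not drop visits. A binary in-window term would remove a graded cycle effect only in part. A visit-order term is not a substitute unless visit 1 was in the window for essentially all women.

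**Cost.** A text correction and a short table of gaps and in-window counts. The documents do not say that onset dates were kept. The sensitivity model uses about 1 error df: (22 − 1) × (3 − 1) = 42 becomes 41, and the critical t moves from 2.018 to 2.020. The main downside is a possibly weaker claim of cycle control.
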